PROTOCOL TITLE:

Promoting ReProductive WellbEing through Shared medical appointments and health coaching Sessions (PROWESS)

PRINCIPAL INVESTIGATOR:

[name], DACM, LAc, FABORM
UH Connor Whole Health
[name]
[contact]

UH FACULTY ADVISOR:

If the principal investigator's primary role at UH is resident, fellow or student, identify a faculty advisor.

N/A

OTHER DEPARTMENTS INVOLVED IN THIS STUDY (IF APPLICABLE):

N/A

DATE:

12/20/2023

1. Objectives

- 1) To examine the feasibility and acceptability of the Whole Health Lifestyle Care for Reproductive Well-being Pilot Program (“Lifestyle Care for Fertility” or LCF) and collection of health behavior and patient-reported outcomes
- 2) To examine the longitudinal changes in health behaviors, and patient reported outcomes of participants in the Lifestyle Care for Fertility program

2. Background

Approximately 10 to 15% of couples are impacted by infertility (1). Struggles with fertility can have a wide range of effects on an individual’s and couple’s life including physical, emotional, sexual, spiritual, and financial aspects. Studies have shown that infertile couples experience significant emotional distress including anxiety, grief, loss, and depression (2). Fertility treatments can be physically demanding and uncomfortable, with side effects including pain, mood changes, headaches, bloating, hot flashes, and sleep disturbance. Recently, research is starting to focus more on diet and lifestyle factors as a way to improve time to pregnancy and therefore lessen the burden of infertility felt by couples (3, 4, 5). Lifestyle factors are the modifiable habits and ways of life that can greatly influence overall health and well-being, including fertility. Many lifestyle factors such as nutrition, weight, exercise, psychological stress, environmental toxins, and others can have substantial effects on fertility.

A combination lifestyle approach is an evidence-based practice in which nutrition, exercise, and integrative therapies such as mindfulness training and stress management have been shown to improve health and well-being, as well as positively impact chronic disease management (6). Evidence shows that patient-centered coaching yields positive results related to lifestyle behaviors (7). Health and wellness coaching (HWC) can provide significant value to patients’ healthcare in the combination lifestyle approach (7). Applying the concept of HWC to fertility patients has the potential to yield improved fertility outcomes, decreased time to pregnancy, and enhanced well-being during the fertility journey, healthier pregnancy as pre-conception is an ideal time to optimize diet and lifestyle habits, and impact future generations with better health and better health habits. This combination lifestyle approach is particularly important for women with polycystic ovarian syndrome (PCOS) which is one of the most common causes of female infertility. International evidence-based guidelines for the management of PCOS include the recommendation of healthy lifestyle behaviors encompassing healthy eating, weight loss, and regular exercise, which are all supported through HWC (8).

3. Inclusion and Exclusion Criteria

| Inclusion Criteria | |
|---------------------------|---|
| 1. | Adult with a uterus aged from 18 to 50 years |
| 2. | Participating in the Lifestyle Care for Fertility program |
| 3. | Able to speak and understand English. |

| | |
|----|---|
| 4. | Has email address and access to mobile device with a functioning data plan. |
| 5. | Infertility-related diagnosis |

| Exclusion Criteria | |
|---------------------------|---|
| 1. | Age < 18 or > 50 years |
| 2. | Having a significant and uncorrected visual, hearing, or cognitive impairment |
| 3. | Inability to provide consent |
| 4. | Current pregnancy |

4. Study Design

This is an observational outcome evaluation of the Lifestyle Care for Fertility program.

5. Study Procedures

Setting

Consent will take place either virtually via telehealth or in a private room at the UH Connor Whole Health (CWH) Beachwood office. The shared medical appointments (SMA) occur at the CWH Beachwood office and the individual Health and Wellness Coaching (HWC) sessions are virtual. Data will be collected via a link to REDCap sent to participants' mobile device.

Participants and Recruitment:

Study participants will be patients of UH CWH who have a fertility-related diagnosis and who are participating in LCF. Patients are referred to the program by their Integrative Medicine provider. The HWC, who is also IRB approved research staff, will then screen program participants for research eligibility and send a recruitment email about the research to those who meet eligibility criteria. Seven days later, the program's HWC will call the patient to tell them about the research study and ask if they are interested to participate. The HWC will make it clear that the patient can participate in the program without participating in the research. If the patient is interested in participating in the research, the HWC will verify that the patient has access to a mobile device with a data plan to complete the study surveys. The coach will then schedule the informed consent with those who have appropriate access.

Consent Process

The consent process begins when the HWC first calls the potential participant and explains the study to them. Interested individuals will schedule a time to meet with the coach or other research staff via telehealth or in person, depending on patient preference and availability, for consent. Potential participants will receive a copy of the informed consent form ahead of time by mail or email and be asked to read it carefully. At the scheduled time via telehealth, the research staff will present the consent form in detail, making sure the participant understands the research by encouraging them to ask any questions they may have, and asking them to explain what the study will involve in their own words. The participant will be given sufficient time to read the informed consent form and the opportunity to ask questions. The patient will be informed that acceptance or refusal to participate in the research will not influence their

ability to receive clinical care, or to participate in the program, and that they are free to withdraw from study participation at any time. Once all of the patient's questions are answered, they will sign an electronic version of the consent form in REDCap, either on their own device or on a study iPad.

For consents conducted via telehealth, research staff will confirm the identity of the patient before signing the consent. Potential participants will confirm their identity by showing his/her driver's license or, if not available, any state or government-issued picture identification card. If they do not have picture identification available, they will be asked to provide the last four digits of the social security number, their date of birth and one of the following: account number, street address, insurance carrier name, insurance policy number, medical record number, birth certificate or insurance card.

Immediately following the consent, the research staff will send participants a REDCap link to complete the demographics form to be completed on the participant's own device or on the study iPad. The remaining baseline surveys will also be sent at this time if the first session is scheduled for within two weeks of the consent appointment. Otherwise the link to the remaining baseline surveys will be sent when it is within two weeks of Session 1.

Intervention Delivery

The program consists of an individual Integrative Health and Medicine (IHM) consultation with a CWH IHM provider, 4 Shared Medical Appointments (SMA) and 4 individual Health and Wellness Coaching (HWC) sessions. The SMA sessions take place at the UH CWH Beachwood office conference and movement rooms. The HWC sessions are virtual. The consultations are either virtual or in person at UH CWH Beachwood.

The following are the topics for each of the 8 weekly sessions:

| Week | Type of Session | Topic |
|-------------|------------------------------------|--|
| 1 | Shared Medical Appointment (SMA) | “NOURISH” with Nutrition experiential and cooking demo. |
| 2 | Health and Wellness Coaching (HWC) | Implement “NOURISH” education into patient’s personal life. |
| 3 | SMA | “MOVE” with Yoga experiential and exercise discussion. |
| 4 | HWC | Implement “MOVE” education into patient’s personal life. |
| 5 | SMA | “REST” with Meditation experiential and sleep discussion. |
| 6 | HWC | Implement “REST” education into patient’s personal life. |
| 7 | SMA | “INTEGRATE” with Acupuncture experiential and supplement discussion. |

| | | | |
|---|-----|---|--|
| 8 | HWC | Implement “INTEGRATE” education into patient’s personal life. | |
|---|-----|---|--|

Participation in the program is not contingent participation in the outcome evaluation. Patients with a uterus aged 18-50 who have a fertility related diagnosis are eligible to participate in the program. Participants in the outcome evaluation will be a subset of the participants in the program who give their consent to researchers to collect survey and EHR data.

Data Collection

Data will be collected at baseline, at 4 weeks, 8 weeks, and before, after, and in between each of the 8 weekly sessions. Data collected at baseline include demographics, PROMIS Sleep Disturbance 8a, Perceived Stress Scale 4 (PSS-4), Infertility Self Efficacy Scale (ISE), and current Health Behaviors (HB). The HB survey will be administered between Sessions 1-8, as well as after Session 8, to observe any longitudinal changes. Patients will complete the PROMIS Sleep Disturbance 8a, PSS-4, and ISE at 4 weeks and 8 weeks. Pre- and post- session data includes 0-10 NRS ratings of stress, energy, focus, wellbeing, perceived support (post-only), and satisfaction (post-only). Additionally, participants will complete a satisfaction survey post Session 8. All data will be collected in REDCap via a text message or email link sent to the participant. Research staff will conduct a review of the participant’s medical record to collect data on the participant’s demographics and clinical characteristics at baseline, and to collect chemical pregnancy data at six months after the 8 sessions have been completed. This data will be entered into REDCap.

6. Study Timeline

| | Consent | Demographics | Baseline | 4 Week | Pre- & Post sessions | Between Sessions/After Session 8 | 8 Week |
|-------------------------------------|-----------|--------------|-----------|----------|--|----------------------------------|----------|
| Estimated time requirement of visit | 30-45 min | 2-3 min | 10-15 min | 8-10 min | Pre: 1 min x 8 Post: 2 min x 7, 6-8 min x 1 | 4-6 min x 8 | 8-10 min |
| Data Collection | | X | X | X | X | X | X |

7. Data to be Collected for Your Study (AFTER consent and HIPAA Authorization have been obtained)

We will collect pre-post outcome measures and satisfaction survey data. Please see attached surveys to be administered. We will also collect the following from the EHR:

- Age
- Sex

- History of mental health dx
- History of use Integrative Health and Medicine services
- Fertility diagnosis
- BMI
- Common comorbidities, including:
 - Hypertension
 - Diabetes
 - Obesity
 - Ischemic heart disease
- Pregnancy as confirmed by presence of human chorionic gonadotropin (hCG) within 6 months of program completion

Attendance data about participants will also be collected.

8. Data Analysis Plan

Acceptability

Patients' responses on the satisfaction survey will be assessed using descriptive statistics.

Feasibility of Study Recruitment and Retention

We will use counts and percentages to summarize recruitment rates (#enrolled/#approached) and pace of accrual for the study, as well as retention rates of study participants (#attended/#enrolled) at each program session.

Demographics and clinical characteristics

We will use descriptive statistics (e.g. means, standard deviations, counts, and percentages) to summarize demographics (e.g., education level, age, income) and clinical characteristics (e.g., fertility-related diagnoses and duration of fertility treatment).

Effects on patient-reported outcomes

Descriptive statistics (e.g. means, standard deviations, counts, and percentages) will be generated for (1) patient-reported outcomes (PRO) collected at baseline, 4 weeks and 8 weeks (2) pre-and post-session NRS measures; and (3) responses to the health behavior survey. We will use linear mixed effects models to assess changes in quantitative measures of perceived stress, sleep disturbance, and self-efficacy over the course of the program. Means and bootstrapped 95% CI will be used to assess single-session effects on numeric rating scale measures of stress, energy, focus, and wellbeing. All statistical analyses will be conducted using R and RStudio.

Data Completeness

Data collected via REDCap at each time point will be evaluated for quality and completeness using reporting functions within REDCap.

9. Risks to Research Participants

Some of the questions might make participants feel uncomfortable. They may skip any questions that they may find upsetting.

There is a slight risk to losing privacy and confidentiality. All paper records will be kept in locked file cabinets and all electronic data will be stored in a password protected database to which only study staff will have access.

10. Provisions to Protect the Privacy Interests of Research Participants

Privacy will be ensured by conducting all study related interactions, including the consent process, within the private spaces, whether that is in person at the UH CWH clinic or remotely.

Confidentiality of the research data will be protected in several ways. Any paper study documents will be stored in locked cabinets within the locked research offices of the PI and/or study staff. Participants will be identified by a separate study ID number on all study records. The lists that link study ID codes with participant names, and all electronic study records will be stored on password-protected, encrypted computers or secure servers. Only aggregate data will be presented or published, and will be presented such that individuals cannot be identified. Only IRB approved study personnel will have access to participant data. All study personnel will be required to be certified in the protection of human subjects throughout the study.

Identifiable information will not be reused or disclosed to any person or entity outside of University Hospitals other than those identified in the protocol, except as required by law, for authorized oversight of the research study, or as specifically approved for use in another study by the IRB.

11. Potential Benefit to Research Participants

There is no guarantee of benefits to any participant in the outcome evaluation, but the knowledge gained may be of benefit to future fertility patients who participate in the program.

12. Withdrawal of Research Participants

The study PI can withdraw participation of research participants at any time without their consent for the following reasons:

- If the subject fails to follow directions for participating in the study;
- If it is discovered that the subject does not meet the study requirements;
- If the study is canceled; or
- For administrative reasons, including competitive enrollment - the target number of subjects has entered the study.

13. Alternatives to Participation

The only alternative to participation in the research is to not participate. Patients can participate in the Lifestyle Care for Fertility program regardless of participation in the research.

14. Drugs or Devices

NA

15. Additional Information

NA

16. Community-Based Participatory Research

NA

17. International information

NA

18. References

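### Does the pregnancy item need a stated opening date and a reference date for participants who stop early?

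*Combined protocol and SAP*

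**What the plan says.** Pregnancy is made operational in two places in the combined protocol and SAP. Section 7 lists it among the health-record items: "Pregnancy as confirmed by presence of human chorionic gonadotropin (hCG) within 6 months of program completion". Section 5, under Data Collection, has research staff review the record "to collect chemical pregnancy data at six months after the 8 sessions have been completed".

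The surrounding text bears on how these are read:

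- Section 3 lists "Current pregnancy" as an exclusion, so a first positive can occur at any time after entry.
- Section 5, Intervention Delivery, introduces the timetable with "The following are the topics for each of the 8 weekly sessions" and numbers the weeks 1 to 8. Four of the eight are shared group appointments.
- Section 5 allows consent to precede Session 1 by more than two weeks: "Otherwise the link to the remaining baseline surveys will be sent when it is within two weeks of Session 1". It sets no upper limit on that gap.
- Section 8 foresees incomplete attendance, since it reports "retention rates of study participants (#attended/#enrolled) at each program session". Section 7 says that attendance is recorded.
- The two objectives in Section 1 cover feasibility and acceptability, and change in health behaviors and patient-reported outcomes. Neither mentions pregnancy, and Section 8 contains no pregnancy summary, denominator or model.

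**The concern.** Completion is the only time anchor for the pregnancy item, and three things are left open.

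1. **Opening date.** A positive hCG at week 3 precedes completion. Read strictly, the wording could leave it out. An early loss that ended before Session 8 is the clearest case, because Section 5 names chemical pregnancy as the target.
2. **Early stoppers.** Someone who leaves after Session 3 has no personal completion date. If one abstractor uses the last attended session, another uses the scheduled end and a third drops the person, any later count depends on attendance, which is itself determined after enrollment.
3. **hCG date.** None is listed for recording, so the report could not separate positives during the program from those after it. The Background also says that coaching "has the potential to yield improved fertility outcomes, decreased time to pregnancy", which might suggest that timing matters.

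At stake would be the consistency and interpretation of a pregnancy proportion, if one were reported.

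**Working it through.** **Inputs.** From the documents: 8 weekly sessions, so 7 weeks (49 days) from Session 1 to Session 8, or 56 days if eight full weeks are counted; and 6 months of follow-up after that. The documents give no sample size, pregnancy rate or dropout rate, so there is no figure of the plan's own to reproduce. Assumed: a constant monthly chance of conception p of 2%, 5% or 10%, and a month of 30.44 days.

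**Formula.** Cumulative chance by month t: C(t) = 1 − (1 − p)^t.

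**Opening date.** With m the program length in months, the share of conceptions that fall in the program weeks is C(m)/C(m + 6).

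- m = 49/30.44 = 1.61, or 56/30.44 = 1.84.
- At p = 5% and m = 1.61: C(1.61) = 7.9%, C(7.61) = 32.3%, share 24.5%.

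| p per month | m = 1.61 | m = 1.84 |
|---|---|---|
| 2% | 22.5% | 24.9% |
| 5% | 24.5% | 27.2% |
| 10% | 28.3% | 31.3% |

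These are upper bounds. They describe omissions only if every in-program pregnancy leaves no hCG record after completion, whereas an ongoing pregnancy may well leave one. If a fraction f leaves none, the omitted share is f times the table entry:

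- f = 10%: 2.2% to 3.1%
- f = 25%: 5.6% to 7.8%
- f = 50%: 11.2% to 15.7%

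**Early stoppers.** Assume 20% stop early, completers conceive at 5% per month, and t = 1.84 + 6 = 7.84 months from Session 1.

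- Completers only: C(7.84) = 33.1%.
- All enrolled: 0.8 × 33.1% + 0.2 × C(7.84) at the stoppers' own rate. This is 30.1%, 33.1% or 37.7% if stoppers conceive at 2.5%, 5% or 10% per month.
- Stoppers counted as not pregnant: 0.8 × 33.1% = 26.5%.

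The completers-only and all-enrolled figures coincide when the two groups conceive at the same rate. A gap between those two, and its direction, comes wholly from an assumed difference in rates. Counting stoppers as not pregnant does lower the proportion whatever their rate, but nothing in the plan calls for that coding.

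**Would a window opening at consent be better?** It would not be one fixed window, because the gap from consent to Session 1 has no limit. At p = 5% and 49 days from Session 1 to Session 8, the cumulative chance to 6 months after Session 8 is:

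| Gap from consent to Session 1 (assumed) | Cumulative chance |
|---|---|
| none | 32.3% |
| 2 weeks | 33.9% |
| 4 weeks | 35.4% |
| 8 weeks | 38.4% |

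That trades dependence on attendance for dependence on consent timing.

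**Does the text leave staff without a usable rule?** Section 5 ties the review to completion of the 8 sessions, and those sessions run weekly on a numbered schedule with group appointments in alternate weeks. Reading completion as the scheduled end of the series gives a calendar date that early stoppers share. The text allows this reading but does not state it. On the hCG date, nobody can judge a 6-month limit without seeing when the test was done, and Section 7 is a list of variables, not a form layout.

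**The case for a change.** The strongest reply is that the sponsor chose to collect pregnancy and follows it longer than anything else, so it should be codable the same way by any two abstractors. Two clarified sentences and a date field, in a chart review already planned, would cost little and would avoid choices made after the data are seen. Much of this stands. The opening date is not stated, the scheduled-end reading is an inference, and writing the rule into the abstraction form is good practice.

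What does not stand is the step from there to a needed amendment. The harm is to a count that the plan does not promise. The time-to-pregnancy argument relies on a Background remark about the potential of coaching, not on a study outcome. The obvious remedy, counting from consent with all enrolled as the denominator, leaves its own questions open: how people with no record in the window are counted, what closes the window for enrollees never scheduled for sessions, and whether chart review continues after withdrawal from the research.

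**Conclusion.** The observation is accurate, but it concerns missing detail and not an error. Following the plan as written makes no planned result or conclusion wrong, because pregnancy is in no objective and no planned analysis of this uncontrolled observational pilot. No bias is shown. Every size above rests on assumed conception and dropout rates. The 22% to 31% share of conceptions in the program weeks is a ceiling that falls to 2% to 16% if 10% to 50% of those pregnancies leave no later hCG record.

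Analysts can fill the gap sensibly: take the scheduled end of the eight weekly sessions as completion for everyone scheduled to start, note the test date that they must consult anyway, and say in any report where counting began and who was in the denominator. No amendment to the plan follows.

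### Health behavior change is part of Objective 2 and is surveyed on 9 occasions, but Section 8 plans only descriptive statistics for it, with no within-person change estimate or interval

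*Combined protocol and SAP*

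**What the plan says.** All references are to the combined protocol and SAP.

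- Section 1, Objective 1 covers feasibility, including "collection of health behavior and patient-reported outcomes". Objective 2 is "To examine the longitudinal changes in health behaviors, and patient reported outcomes of participants in the Lifestyle Care for Fertility program".
- Section 2 cites evidence that "patient-centered coaching yields positive results related to lifestyle behaviors".
- Section 4: "This is an observational outcome evaluation of the Lifestyle Care for Fertility program".
- Section 5, Data Collection, includes current health behaviors in the baseline set and continues: "The HB survey will be administered between Sessions 1-8, as well as after Session 8, to observe any longitudinal changes". For the three scales: "Patients will complete the PROMIS Sleep Disturbance 8a, PSS-4, and ISE at 4 weeks and 8 weeks", in addition to baseline.
- Section 6 budgets 4 to 6 minutes, 8 times, for the surveys between sessions and after Session 8.
- Section 7 refers to the instruments as attachments: "Please see attached surveys to be administered". The HB survey is not in the available text.
- Section 8, Effects on patient-reported outcomes, promises descriptive statistics (an open list of examples: means, SDs, counts, percentages) for three groups: the patient-reported outcomes, the session ratings and the HB responses. It then adds "linear mixed effects models to assess changes in quantitative measures of perceived stress, sleep disturbance, and self-efficacy over the course of the program", and means with bootstrapped 95% confidence intervals for single-session effects on stress, energy, focus and wellbeing. It says nothing further about HB.

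**The concern.** Health behavior is one of the two outcome groups in Objective 2, and lifestyle behavior is what the Background expects coaching to improve. The plan repeats the HB survey expressly to see change over time, yet it is the only one of the three groups in Section 8 for which no measure has an analysis of change.

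A table of means and SDs, or percentages, by occasion is not a substitute. The precision of a within-person change depends on how strongly a person's answers at two times are correlated, and such a table leaves that out. If different people answer at different occasions, adjacent columns also compare partly different groups. At stake is whether the HB part of Objective 2 is reported with any statement of uncertainty, and whether the choice of items and time points to highlight is made only after the data are seen.

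**Working it through.** **1. Number of occasions.** Section 5 gives 1 at baseline, one in each gap between Sessions 1 and 8, and 1 after Session 8. Eight sessions have 7 gaps, so follow-ups = 7 + 1 = 8, which reproduces the factor of 8 in the Section 6 timeline. Total = 1 + 8 = 9. The plan does not state 9, but text and table agree on it. The sleep, stress and self-efficacy scales have 3 occasions (baseline, 4 weeks, 8 weeks).

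**2. Share of participants' survey time after baseline (Section 6).**
- HB: 8 × 4 to 8 × 6 = 32 to 48 min.
- Before and after sessions: 8 × 1 + 7 × 2 + (6 to 8) = 28 to 30 min.
- 4 and 8 weeks: 2 × 8 to 2 × 10 = 16 to 20 min.
- Total: 76 to 98 min.
- HB share: 32/76 = 42% to 48/98 = 49%. Mixing low and high ends gives 32/82 = 39% to 48/92 = 52%.

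**3. What Section 8 commits to.**

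| Group | Descriptive | Analysis of change | Interval named |
|---|---|---|---|
| Stress, sleep, self-efficacy scales | yes | mixed models | no |
| Stress, energy, focus, wellbeing ratings (pre and post) | yes | single-session mean | bootstrapped 95% CI |
| Perceived support, satisfaction ratings (post only) | yes | none | no |
| HB survey | yes | none | no |

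The post-only ratings have no pre-session value, so a single-session change cannot be formed for them. HB has a baseline and 8 follow-ups.

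**4. Illustration of precision.** The documents give no sample size, correlation or HB scoring. Everything here is assumed: continuous score, equal SDs, n people answering at baseline and after Session 8, correlation r between the two answers.

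Half-width of the 95% CI, in SD units = t(0.975, n−1) × √(2(1−r)/n).

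For n = 30, t = 2.045:
- r = 0.7: 2.045 × √(0.6/30) = 2.045 × 0.1414 = 0.289.
- r = 0.5: 2.045 × √(1/30) = 2.045 × 0.1826 = 0.373.

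| n | r = 0.7 | r = 0.5 |
|---|---|---|
| 15 | 0.429 | 0.554 |
| 30 | 0.289 | 0.373 |
| 50 | 0.220 | 0.284 |

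For a yes/no item at 50% both times, a rough normal approximation is 1.96 × √(0.5(1−r)/n). With n = 30 this gives 13.9 points (r = 0.7) to 17.9 points (r = 0.5).

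**5. The same table with different precision.** With n = 30 and means 0.40 SD apart, the interval is 0.40 ± 0.29 = 0.11 to 0.69 at r = 0.7, and 0.40 ± 0.37 = 0.03 to 0.77 at r = 0.5. The means and SDs are identical, but the second interval is √(0.5/0.3) = 1.29 times as wide. A reader of the descriptive table could not tell which applies.

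**The case against.** The strongest case for the plan is that description is enough here. Objective 2 says examine, and the HB survey is there to observe change. This is an observational evaluation of a pilot program with feasibility as its first objective, and it states no HB hypothesis, test or success criterion. Section 8 limits the mixed models to quantitative measures, so modelling the scored scales and describing an unscored checklist may be a deliberate split. The HB survey cannot be seen here, so that cannot be ruled out. The descriptive list is also open, and a change score would fit within it.

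Most of this stands as a limit on weight. It does not remove the point. Non-quantitative items would explain leaving HB out of a linear model, but not the absence of any change estimate, since a paired change in proportion with an interval works for yes/no items. An open list permits a change score without committing to one. The same pilot already goes beyond description for its other repeated measures.

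Three stronger readings are tempting and are not supported:

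- **That every other measure has an interval.** Section 8 names none for the mixed models and none for the post-only ratings. The contrast is with modelled change for the scales and with bootstrapped intervals for four ratings.
- **That the missing interval could reverse the conclusion.** In the 0.40 SD example with 30 people, both intervals at r = 0.5 to 0.7 exclude zero. Including zero would take a correlation between baseline and last answers close to none: serial decay of 0.5 to 0.7 per occasion gives 0.004 to 0.058 after 8 steps, and half-widths of 0.53 to 0.51. No passage supports such decay.
- **That HB results will be biased by nonresponse.** Section 9 lets participants skip questions, but nothing shows selective response. The Data Completeness paragraph of Section 8 already plans checks at each time point, although it does not promise to report the counts.

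**Conclusion.** The point holds, with modest weight. It is certain from the text that HB change is part of Objective 2, that the survey is given on 9 occasions, and that Section 8 commits only to descriptive statistics for it. It follows that HB results could be presented as a trend with no statement of how precise the within-person change is.

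The size cannot be fixed from the documents. Under the stated assumptions the unreported uncertainty would be about ±0.29 to ±0.37 SD with 30 people, and ±0.22 to ±0.55 SD across 15 to 50 people. These figures show the order of magnitude and are not estimates for this study.

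A reader might infer that the plan cannot address Objective 2 for health behaviors, or that its HB results will be wrong. Neither follows: description addresses the objective in part, and no bias is claimed. The change is worth making because it uses data already being collected and methods that Section 8 already names.

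**What to change.** Add to Section 8:

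- Within-person HB change from baseline to after Session 8 will be estimated with a 95% confidence interval, for the HB score or, if there is no score, for every HB item or for a list of items fixed before the data are examined.
- The estimate will come from a mixed model suited to the item type (linear, ordinal or binary), fitted to all available occasions. If the model does not converge, the paired change in mean or proportion will be reported with the bootstrapped 95% interval already used in Section 8.
- The descriptive table by occasion stays, with the number responding at each occasion taken from the completeness checks already planned.
- The HB intervals are exploratory and not adjusted for multiplicity.

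The cost is a few sentences and some R code, with no new data. There are four drawbacks. Without a score there will be several unadjusted intervals. Sparse items may need collapsing. The paired fallback uses only two of the nine occasions and drops anyone missing either one. Percentile bootstrap intervals also run slightly narrow in very small samples: for a normally distributed change, coverage is roughly P(|t with n−1 df| < 1.96 × √((n−1)/n)), which is 92.1% at n = 15, 93.6% at n = 30 and 94.2% at n = 50.
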